**Table 7.6.4.2-1: Selected Pre-Malignant Lesions**

---

**Serious and non-serious AEs: preferred terms in MedDRA dictionary**

Actinic keratosis, Adrenal cortex dysplasia, Anogenital dysplasia, Blood disorder, Breast dysplasia, Bronchial dysplasia, Cervical dysplasia, Dysplasia, Endometrial dysplasia, Epidermodysplasia verruciformis, Erythroplasia of lipa, Erythroplasia of penisa, Erythroplasia of vulvaa, Focal nodular hyperplasiaa, Gastric dysplasia, Gastrointestinal dysplasia, Hepatic dysplasia, Laryngeal dysplasia, Leukoplakia, Myeloid metaplasiaa, Nodular regenerative hyperplasia, Oesophageal dysplasia, Olfactory genital dysplasia, Palatal dysplasia, Penile dysplasia, Placental dysplasia, Precancerous skin lesion, Prostatic intraepithelial neoplasia, Queyrat erythroplasiaa, Tongue dysplasia, Vaginal dysplasia, Vulvar dysplasia.

---

aTerms derived from the neoplasms SOC.

### 7.6.5 Overall Adverse Events

AEs are summarized by intensity (All Grades; All Grades related; Grade 2 - 4 related; Grade 3 - 4) and treatment regimen for the following 3 cohorts:

- Through Week 48 on blinded therapy for treated subjects
- After Week 48 on blinded therapy or on open-label ETV through Week 96 for the Year 2 Safety Cohort
- On ETV treatment for the All ETV Safety Cohort

If relationship to study therapy is missing, the AE is included in summaries of AEs related to study therapy.

AEs are also summarized by intensity (All Grades) and treatment regimen during (1) off-treatment follow-up for off-treatment follow-up subjects in the Post-Year 1 Safety Cohort, (2) alternative ETV follow-up for alternative ETV follow-up subjects in the Post-Year 1 Safety Cohort, and (3) long-term follow-up for long-term follow-up subjects in the Post-Year 1 Safety Cohort.

On-treatment non-serious AEs (All Grades) occurring with incidence  $\geq 5\%$  on any treatment regimen are also summarized analogously for the 3 cohorts. Multiple on-treatment non-SAEs (All Grades) occurring with incidence  $\geq 5\%$  on any treatment regimen are also summarized for the 3 cohorts, presenting the numbers of events and exposure-adjusted incidence rates (see [Section 8.10](#)).

Multiple on-treatment AEs (All Grades) occurring with incidence  $\geq 5\%$  on any treatment regimen are also summarized for the 3 cohorts, presenting the numbers of events and exposure-adjusted incidence rates (see [Section 8.10](#)).

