Procedure	Screening ≤ 6 Weeks prior to Randomization	Randomize Initiate study drug (Day 1) within 72 hours	On Study Treatment Weeks 4, 8, 12 ± 3 days, and every 12 weeks ± 5 days up to end of study drug dosing	Weeks 52, 100 and 148 ± 10 days (if needed) ^a	End of Treatment (Scheduled or Early)	Observational LTFU ^b Weeks 6, 12, and every 12 weeks ± 5 days Up to 264 weeks total study participation [or 48 weeks beyond completion of rescue open- label ETV used for treatment of an extreme elevation of ALT due to acute exacerbation of CHB; whichever is later]	Protocol Section
Specimens for Resistance Testing (3 mL)		X	Week 48, 96, 144 ^j		X		6.9
Other Assessments							
Sparse PK (2 ml) ^k			Weeks 4, 12, 24, 48				
Semi-intensive PK (8 ml) ^l			Week 4				
Clinical Drug Supplies							
Dispense Study Medication		X	X	X		X ^d	5.2
Assessment of Study Medication Use			X	X	X	X ^d	5.6

- ^a Assessments of seroconversion will be made based on serology results at Weeks 48, 96, and 144. Study drug will be modified, continued, or discontinued according to the study schema (Section 4.1).
- ^b Only protocol required visits and assessments are mentioned. Subjects placed on rescue open-label ETV to treat an extreme elevation of ALT due to acute exacerbation of CHB should undergo additional non-protocol visits and assessments at investigator discretion.
- ^c Histological results will be documented for subjects who have had a prior liver biopsy.
- ^d For subjects receiving rescue open-label ETV to treat an extreme elevation of ALT due to acute exacerbation of CHB only.
- ^e Adverse events should be recorded at week 6 for all subjects enrolled in LTFU, and at each visit for subjects receiving rescue open-label ETV.
- ^f Volume of blood to be collected may vary based on available specimen collection tubes.
- ^g While on study treatment.
- ^h WOCBP only. Additional home pregnancy testing will be required in between study visits starting from Week 18 and every 12 weeks thereafter while on study treatment.
- ⁱ All subjects enrolled in LTFU should undergo pregnancy testing at week 6. Subjects receiving rescue open-label ETV should be tested every 6 weeks during treatment and 6 weeks after the last dose of study medication (home pregnancy tests should be used in between study visits).
- ^j For subjects still on study ETV only (Section 6.9.2).

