7.3.3 Nonserious Adverse Events

The collection of nonserious AE information should begin at initiation of study drug. Nonserious AE information should also be collected from the start of a placebo lead-in period or other observational period intended to establish a baseline status for the subjects. During the long-term follow up phase, Adverse Events related to the administration or discontinuation of study drug should be documented for subjects that are not receiving commercially available anti-HBV therapy. Also during the LTFU phase, all adverse events should be documented in subjects receiving rescue open-label ETV.

If an ongoing nonserious AE worsens in its intensity or its relationship to the study drug changes, a new nonserious AE entry for the event should be completed. Nonserious AEs should be followed to resolution or stabilization, or reported as SAEs if they become serious (see Section 7.3.1). Follow-up is also required for nonserious AEs that cause interruption or discontinuation of study drug, or those that are present at the end of study treatment as appropriate.

All identified nonserious AEs must be recorded and described on the appropriate nonserious AE page of the CRF (paper or electronic).

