### 6.3 Populations for Analyses

- **Enrolled subjects** are those who sign an informed consent form and are assigned a Patient Identification number (PID). This cohort is used to assess subject disposition, deaths and serious adverse events during the **pre-treatment period**.
- **Randomized subjects** are enrolled subjects who receive a treatment assignment from the central randomization center. This cohort is used to assess subject status and accrual.
- **Treated subjects** are randomized subjects who receive at least 1 dose of study therapy. This cohort is used to assess all data domains.
  - **Primary cohort** is defined as at least the first 123 subjects randomized and treated. The Primary Cohort is used for the primary analyses.
- **Off-treatment follow-up subjects** are treated subjects who discontinue study therapy and have at least 1 of the following assessments during the **off-treatment follow-up period** (see [Section 6.1](#)): death date if it exists; adverse event onset date; HBV related diagnosis date; vital signs date; physical measurement date; physical exam date; neurologic exam date; laboratory test date (safety, pregnancy, serology and virology); liver biopsy date; Tanner staging date. This cohort is used to assess safety during the off-treatment follow-up period.
- **Long-term follow-up subjects** are treated subjects who discontinue study therapy and have at least 1 of the following assessments during the **long-term follow-up period** (see [Section 6.1](#)): death date if it exists; adverse event onset date; HBV related diagnosis date; vital signs date; physical measurement date; physical exam date; neurologic exam date; laboratory test date (safety, pregnancy, serology and virology); liver biopsy date; Tanner staging date. This cohort is used to assess safety during the long-term follow-up period.
- **Alternative ETV follow-up subjects** are treated subjects who discontinue study therapy, receive at least 1 dose of alternative ETV therapy, and have at least 1 of the following assessments during the **alternative ETV follow-up period** (see [Section 6.1](#)): death date if it exists; adverse event onset date; HBV related diagnosis date; vital signs date; physical measurement date; physical exam date; neurologic exam date; laboratory test date (safety, pregnancy, serology and virology); liver biopsy date; Tanner staging date. This cohort is used to assess safety during the alternative ETV follow-up period.

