## **7.6 Safety**

The investigators determine the intensity of AEs and the relationship of AEs to study therapy. The investigators' terms are coded and grouped by system organ class using the latest version of the Medical Dictionary for Regulatory Activities (MedDRA) in production at BMS.

In order to account for AEs with multiple occurrences in the same subject, AE records are collapsed for each subject and preferred term when records have the same onset date, or when records are contiguous or overlapping (see [Section 8.10](#)). All AE presentations are based on collapsed records.

AEs are presented by system organ class and preferred term, both in descending order of incidence on ETV, unless specified otherwise.

AE presentations include both non-serious and SAEs as defined in the protocol, unless specified otherwise. If a subject had an AE with different intensities during the study period, then only the greatest intensity is reported.

On-treatment safety is assessed for the following 3 cohorts (see [Sections 6.1](#) and [6.3](#)):

- Through Week 48 on blinded therapy for treated subjects
  - ETV and PBO are assessed on treatment up to the Week 48 cut, ie, the earlier of (a) 54 weeks, the upper bound of the Week 48 visit window (see [Section 8.4](#)), and (b) the first dose of open-label ETV.
- After Week 48 on blinded therapy or on open-label ETV through Week 96 for the Year 2 Safety Cohort

- ETV, PBO BL and PBO OL are assessed on treatment after the Week 48 cut and up to 102 weeks, the upper bound of the Week 96 visit window (see [Section 8.4](#)).
- On ETV treatment for All ETV Safety Cohort

Note that AEs with onset on the first day of study therapy are considered on treatment, AEs with onset on the first day of ETV are considered on ETV treatment and AEs with onset on the first day of open-label ETV are considered on open-label ETV.

Follow-up safety is assessed for the following 3 cohorts (see [Sections 6.1](#) and [6.3](#)):

- During off-treatment follow-up for off-treatment follow-up subjects in the Post-Year 1 Safety Cohort
- During long-term follow-up for long-term follow-up subjects in the Post-Year 1 Safety Cohort.
- During alternative ETV follow-up for alternative ETV follow-up subjects in the Post-Year 1 Safety Cohort (select endpoints only).

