- Dose end date of active ETV is the dose end date of study therapy for ETV-randomized subjects and the dose end date of open-label ETV for PBO-randomized subjects. This date is used to assess time on active ETV.
- Last dose date of active ETV is the dose end date of active ETV derived only when the last dose date of study therapy is not missing.
- Start date of rescue open-label ETV is the earliest start date of rescue open-label ETV identified from valid dosing records, ie, non-missing start date and total dose > 0, from rescue open-label ETV study medication CRFs.
- Start date of alternative ETV therapy is the earliest start date of (1) rescue open-label ETV, or (2) concomitant ETV taken on treatment or during long-term follow-up.
- Start date of alternative anti-HBV therapy is the earliest start date of (1) rescue open-label ETV, or (2) concomitant anti-HBV medication taken on treatment or during long-term follow-up.
- Last contact date is the death date, if it exists, or the latest of the following dates: randomization; first or last dose of study therapy; adverse event onset or resolution; hepatitis B related diagnosis; laboratory test (safety, pregnancy, serology and virology); liver biopsy; physical measurement; physical exam; neurologic exam; vital sign; non-study medication start or stop; last contact from end of treatment or end of study subject status; Tanner staging.

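### All-grade AE percentages in alternative-ETV and long-term follow-up pool children under three different AE collection rules, so they can only equal or understate true incidence

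*SAP*

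**What the plan says.** **Analysis.** SAP 7.6.5 states that "AEs are also summarized by intensity (All Grades) and treatment regimen during" three follow-up periods. The first is off-treatment follow-up; the others are given as "2) alternative ETV follow-up for alternative ETV follow-up subjects in the Post-Year 1 Safety Cohort, and (3) long-term follow-up for long-term follow-up subjects". SAP 7.6 sets the default content: "AE presentations include both non-serious and SAEs as defined in the protocol, unless specified otherwise".

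**Who is in the tables.** SAP 8.9 reads: "Start date of alternative ETV therapy is the earliest start date of (1) rescue open-label ETV, or (2) concomitant ETV". Alternative ETV is therefore rescue drug supplied by the sponsor or any non-study ETV. Under SAP 6.3, alternative-ETV subjects must have stopped study therapy, "receive at least 1 dose of alternative ETV therapy, and have at least 1 of the following assessments during the" period; a laboratory test or a vital-signs date is enough. The long-term follow-up cohort has the same kind of entry rule, without the ETV condition. Under SAP 6.1 both periods run to the end of the study. Only off-treatment follow-up is cut the day before alternative anti-HBV therapy starts, and rescue ETV counts as such therapy.

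**Collection.** Protocol 6.3.2 and 7.3.3 have AEs related to giving or stopping study drug "documented for subjects that are not receiving commercially available anti-HBV therapy". Section 7.3.3 adds that every AE is documented for children on rescue open-label ETV. SAEs and HBV-related diagnoses are reported in LTFU whatever the therapy (Protocol 6.3.2). Footnote e to Protocol Table 6.1 says: "Adverse events should be recorded at week 6 for all subjects enrolled in LTFU, and at each visit for subjects receiving rescue open-label ETV". Protocol 4.1.1 lets clinicians use marketed anti-HBV products in LTFU.

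**The concern.** A percentage of subjects with any AE means what it says only if everyone in the denominator could have had an AE recorded. In these two tables many children could reach the numerator only through an SAE, a study-drug-related event or the Week 6 visit. A reader would take lack of collection for lack of events.

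Long-term pediatric safety is a stated secondary objective (Protocol 2.2, SAP 3.2), and SAP 9 makes follow-up safety the minimum content of the final analysis. The tables are also split by regimen (SAP 6.3, Post-Year 1 Safety Cohort). If use of commercial therapy differs between those groups, comparisons across columns would partly reflect collection rules.

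**Working it through.** The plan gives no follow-up AE rate and no number of children on rescue or commercial therapy, so there is no figure to reproduce. The check sets the collection rules beside the table definitions and then illustrates the size.

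**Step 1: what can be captured in LTFU**

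| Status in LTFU | Non-serious AEs documented | SAEs and HBV-related diagnoses | Source |
|---|---|---|---|
| Receiving rescue open-label ETV | All, at each visit | Yes | Protocol 7.3.3, footnote e |
| Not on rescue, not on commercial therapy | Study-drug-related; AEs at Week 6 | Yes | Protocol 6.3.2, 7.3.3, footnote e |
| On commercial therapy | AEs at Week 6 only | Yes | Protocol 6.3.2, 7.3.3, footnote e |

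Protocol 7.4 also sends some laboratory abnormalities to the AE page.

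**Step 2: what each table pools**

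- *Alternative-ETV follow-up* mixes the first and third rows, because its definition includes concomitant ETV. It also includes time after rescue ends. Rescue lasts up to 96 consecutive weeks, and the child then stays on study for at least 48 more (Protocol 4.1.2). With a full course, at least 48/(96 + 48) = one third of the time from rescue start lies outside full collection; with a shorter course the minimum share is larger.
- *Long-term follow-up* mixes all three rows, because it is not cut at alternative therapy.
- *Off-treatment follow-up* stays within the second row, because it stops before rescue or other anti-HBV therapy.

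**Step 3: direction.** Captured events are a subset of the events that occur, and the denominator is the same whether or not events are captured. The tabulated percentage is therefore at most the true all-grade incidence in that cohort.

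**Step 4: illustrative size for the alternative-ETV table.** All inputs are assumed. Let t be the true any-AE risk, taken as equal in both groups; s the risk captured without full collection, mainly SAEs; and c the share of the cohort on commercial ETV. Then

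shown = (1 - c) × t + c × s.

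With t = 60%:

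| c | s = 5% | s = 10% | Shown / true |
|---|---|---|---|
| 25% | 45.0 + 1.25 = 46.25% | 45.0 + 2.5 = 47.5% | 0.77-0.79 |
| 50% | 30.0 + 2.5 = 32.5% | 30.0 + 5.0 = 35.0% | 0.54-0.58 |
| 75% | 15.0 + 3.75 = 18.75% | 15.0 + 7.5 = 22.5% | 0.31-0.38 |

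Over a wider grid (t of 50% or 70%, s of 5% or 10%, c from 25% to 90%) the table shows about 16% to 80% of the true rate. The lowest case is t = 70%, s = 5%, c = 90%: 0.10 × 70 + 0.90 × 5 = 11.5%, and 11.5/70 = 0.16. The highest is t = 50%, s = 10%, c = 25%: 0.75 × 50 + 0.25 × 10 = 40%, and 40/50 = 0.80.

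**The case against.** The strongest reply is that these are descriptive follow-up tables with no planned test. The secondary AE endpoint runs through Week 48, SAEs are tabulated separately for the same cohorts (SAP 7.6.2), and SAP 7.6.5 already includes an off-treatment table cut before alternative therapy. Table formats are left to a Data Presentation Plan that is not among the documents and might carry a footnote. All of this stands and limits the stakes. It does not remove the bias from the other two tables: the SAP text sets their cohorts and content. The phrase on number evaluable in SAP 7.1 is neither defined for AEs nor tied to collection.

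Several stronger readings are tempting but unsupported:

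- *Non-serious AEs are simply not collected outside rescue.* Week 6 recording covers everyone, and related AEs are documented for children not on commercial therapy.
- *The table flatters ETV given after a severe flare.* Only rescue requires an extreme ALT elevation (Protocol 4.1.2). Other ETV in LTFU is at the clinician's discretion, so the cohort is not a post-flare population.
- *Footnote e contradicts Protocol 6.3.2 and 7.3.3.* The footnote annotates scheduled assessments and does not exclude documenting related events at other times. The passages are ambiguous, and sites could apply them differently.
- *Laboratory tables share the flaw.* Hematology and chemistry are scheduled for all LTFU subjects (Protocol Table 6.1), and SAP 7.6.6 uses subjects with at least one measurement as the denominator.

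**Conclusion.** The concern holds for the all-grade AE summaries in alternative-ETV and long-term follow-up. As written, they place children under full, partial and SAE-only collection over one denominator, and the resulting percentages can only equal or fall below true incidence. The direction follows from the documents alone. The size does not: it depends on the split between rescue and commercial therapy, the true AE risk and the risk captured without full collection, none of which is given. The 60% example is an illustration and not an estimate.

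Off-treatment follow-up does not mix the levels, but its all-grade label also promises more than is collected. SAE tables, laboratory-abnormality tables, on-treatment AE tables and the Week 48 AE endpoint are unaffected. The change is worth making because it is cheap and removes a bias of known direction from the long-term safety report.

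**What to change.** 1. **Alternative-ETV follow-up:** report all-grade AEs only for rescue open-label ETV subjects and only for time on rescue. Use the rescue start date already derived in SAP 8.9 and add a derived rescue end date from the same dosing records. The alternative-ETV start date will not serve, since concomitant ETV may come first. For concomitant or commercial ETV, and for time after rescue, report SAEs only. Restricting by person alone would be insufficient, because the period runs to the end of the study.
2. **Long-term follow-up:** report SAEs and HBV-related diagnoses for the full cohort. Leave non-serious AEs to the off-treatment table and the rescue-time table. Cutting the long-term table at commercial therapy would largely repeat the off-treatment table and still mix all-AE with related-AE collection.
3. **Off-treatment follow-up:** keep the table, but label its non-serious content as study-drug-related AEs plus Week 6 recording.
4. Footnote the collection rule on every follow-up AE table.
5. Leave the laboratory-abnormality tables as planned.
6. Reconcile footnote e of Protocol Table 6.1 with Protocol 6.3.2 and 7.3.3, so that sites apply one rule.

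The cost is SAP wording, one derived date, table footnotes and a protocol clarification; no new data are needed. The downside is smaller denominators in some descriptive tables.

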6.3.2 Adverse Event Monitoring

Subjects will be closely monitored throughout the study for adverse events. Subjects who have study medication completed or discontinued permanently must be followed for the full 5 years of the study.

During the dosing phase, palatability issues with respect to the oral solution (placebo or active drug) should be reported as Adverse Events.

During the observational long-term follow up phase, Adverse Events related to the administration or discontinuation of study drug should be documented for subjects that are not receiving commercially available anti-HBV therapy. Serious Adverse Events and HBV-related diagnoses should be reported during the long-term follow up phase, regardless of whether or not the subjects are receiving commercially available anti-HBV therapy.

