## 6 STUDY PERIODS, TREATMENT REGIMENS AND POPULATIONS FOR ANALYSES

### 6.1 Study Periods

Study periods for efficacy and safety analyses are defined as follows:

- **Pre-treatment period** begins at the first visit until initiation of study therapy.
- **On-treatment period** begins after the first day of study therapy and ends at the last dose of study therapy plus 5 days.
- **ETV treatment period** begins after the first day of active ETV and ends at the last dose of active ETV plus 5 days.
- **Off-treatment follow-up period** begins on the last dose of study therapy plus 6 days and ends at the start of alternative anti-HBV therapy minus 1 day.
- **Long-term follow-up period** begins on the last dose of study therapy plus 6 days until the end of the study.
- **Alternative ETV follow-up period** begins on the later of the last dose of study therapy plus 6 days and the start of alternative ETV therapy, until the end of the study.

Note that rescue open-label ETV is considered alternative anti-HBV therapy. See [Section 8.9](#) for additional conventions.

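### The all-grade AE tables for alternative-ETV and long-term follow-up pool children under different non-serious AE collection rules, so the non-serious percentages are biased downward to the extent that children use commercial anti-HBV therapy.

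*SAP*

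**What the plan says.** SAP 7.6.5 gives three follow-up summaries of all-grade AEs: (1) off-treatment follow-up, then "2) alternative ETV follow-up for alternative ETV follow-up subjects in the Post-Year 1 Safety Cohort, and (3) long-term follow-up for long-term follow-up subjects". SAP 7.6 sets the content: "AE presentations include both non-serious and SAEs as defined in the protocol, unless specified otherwise".

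Under SAP 6.1 the long-term follow-up period "begins on the last dose of study therapy plus 6 days until the end of the study". The alternative-ETV period starts at whichever of two dates comes second: "the last dose of study therapy plus 6 days and the start of alternative ETV therapy, until the end of the study". Only off-treatment follow-up, table (1), ends the day before alternative anti-HBV therapy starts. SAP 8.9 pools two sources of supply: "Start date of alternative ETV therapy is the earliest start date of (1) rescue open-label ETV, or (2) concomitant ETV". Under SAP 6.3, a single dated assessment in the period, such as one laboratory test, puts a treated child into the cohort.

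The protocol's collection rules for long-term follow-up (LTFU) are narrower. Section 6.3.2 says: "Adverse Events related to the administration or discontinuation of study drug should be documented for subjects that are not receiving commercially available anti-HBV therapy". Section 7.3.3 repeats this and adds that "all adverse events should be documented in subjects receiving rescue open-label ETV". SAEs and HBV-related diagnoses are reported whatever therapy the child receives (6.3.2; for SAEs also 7.3.1). Footnote e to Table 6.1 has AEs recorded at LTFU Week 6 for all subjects, and at each visit for those on rescue ETV. Section 4.1.1 allows marketed or investigational anti-HBV products during LTFU.

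**The concern.** An incidence percentage needs a numerator and a denominator observed under the same rule. Here a child who moves to commercial therapy stays in the denominator to study end, but that child's non-serious AEs are largely no longer requested. The table treats what was not collected as not having happened.

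Long-term safety of ETV in children is a secondary objective (Protocol 2.2, SAP 3.2). Table (2) is the only all-grade AE summary for ETV given after study therapy. Read as it stands, its percentage reflects the mix of rescue and commercial supply as well as tolerability, and it looks better the more commercial ETV is used. In table (3), regimen groups would also stop being comparable if commercial use differed between them.

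**Working it through.** The plan states no figure to reproduce. The check sets what is counted against what is collected, and then looks at direction and possible size.

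**Step 1: collection against counting.**

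| Child's status in LTFU | Non-serious AEs collected (Protocol 6.3.2, 7.3.3, Table 6.1 note e) | In table (2)? | In table (3)? |
|---|---|---|---|
| On sponsor rescue ETV | All | Yes | Yes |
| After rescue, no other therapy | Study-drug-related only | Yes, to study end | Yes |
| No therapy, never on alternative ETV | Study-drug-related only, plus the Week 6 visit | No | Yes |
| On commercial ETV | None by rule, except the Week 6 visit | Yes | Yes |
| On another commercial anti-HBV drug, never on alternative ETV | None by rule, except the Week 6 visit | No | Yes |

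The SAP gives no restriction, censoring, split or footnote for either table. Exposure-adjusted rates in SAP 7.6.5 cover only the three on-treatment cohorts, so nothing offsets the unobserved time.

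**Step 2: how much the Week 6 visit recovers.** LTFU visits fall at Weeks 6 and 12 and then every 12 weeks, up to study Week 264. For a child stopping study drug at Week E, LTFU lasts 264 − E weeks and has 1 + (264 − E)/12 visits.

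- E = 96: 168 weeks and 15 visits. Week 6 is 1/15 = 6.7% of visits and 6/168 = 3.6% of the time.
- E = 144: 120 weeks and 11 visits. Week 6 is 1/11 = 9.1% of visits and 6/120 = 5.0% of the time.
- E = 192: 72 weeks and 7 visits. Week 6 is 1/7 = 14.3% of visits and 6/72 = 8.3% of the time.

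In table (2) the visit helps only if alternative ETV had started by then.

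**Step 3: direction and illustrative size, non-serious AEs only.** Let T be the true percentage with a non-serious AE, f the share of the denominator on commercial therapy, and c the share of those children with such an AE who are still captured. If risk is equal across groups and everyone else is fully captured:

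reported = T × [1 − f(1 − c)]

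This is below T whenever f > 0 and c < 1. The documents give none of T, f or c, so all three are assumed. With T = 40%:

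| c | f = 0.1 | f = 0.3 | f = 0.5 | f = 0.8 |
|---|---|---|---|---|
| 0 | 36.0% | 28.0% | 20.0% | 8.0% |
| 1/7 | 36.6% | 29.7% | 22.9% | 12.6% |
| 0.25 | 37.0% | 31.0% | 25.0% | 16.0% |

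For example, with c = 1/7 and f = 0.5: 40 × [1 − 0.5 × 6/7] = 22.9%. The value c = 1/7 is the largest Week 6 visit share from Step 2. The value c = 0.25 allows for other routes of capture.

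The identity suits table (2) best. In table (3) the remaining children are not fully captured either, and events before commercial therapy starts can count.

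**Step 4: the all-grade percentage.** SAEs are collected from everyone and count in the all-grade rate. With true all-grade incidence p and SAE incidence s, and again with everyone else fully captured, the displayed rate is at least p(1 − f) + s × f. The relative loss is therefore smaller than for non-serious events alone.

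**The case against.** The case on the other side has four parts.

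*Collection is not nil.* Week 6 AEs are recorded for every LTFU subject. Protocol 7.4 sends clinically significant laboratory results to the AE pages, and 7.7 does the same for significant worsening on examination, neither with a therapy restriction. This stands. A reader might infer that no non-serious AE can be scored once a child is on commercial therapy; the documents do not support that.

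*The plan already has a clean table.* Table (1) stops before alternative therapy and follows the follow-up period in Protocol 8.4.2. This also stands, and it means that simply cutting table (3) at commercial therapy would largely repeat table (1). It does not repair tables (2) and (3), which are reported as well.

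*Other safety outputs exist.* SAP 7.6.2 has an SAE table for alternative-ETV follow-up, and 7.6.6.1 summarizes laboratory abnormalities there. On-treatment AEs, disease progression, neoplasms and growth do not depend on the two tables. So table (2) is not the only safety information on post-study ETV, and the SAE data there are complete by rule.

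*The tables are descriptive.* No hypothesis is tested on them. That limits the consequence, but an uncaveated all-grade percentage will still be read as an incidence.

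**Conclusion.** The mismatch holds for both tables. If any child in the denominator uses commercial anti-HBV therapy, the non-serious AE percentage is biased downward, and each table mixes collection rules. The size cannot be computed from the documents. The figures above assume T, f and c, equal AE risk across groups, and full capture in everyone else. SAE tables are not affected.

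Two stronger readings should be resisted. One might take the displayed all-grade rate to be p(1 − f); SAEs, Week 6 AEs and, in table (3), events before commercial therapy still count, so it is not. One might also infer a high commercial share from the planning rates (20% ETV response, 10% placebo seroconversion). Those are planning assumptions for Week 48, while ETV may continue to Week 144 or 192, and they say nothing about rescue versus commercial supply among alternative-ETV users.

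The gap is also not confined to commercial users. Untreated children have only study-drug-related AEs documented after Week 6, so an all-AE percentage in table (3) is incomplete for them too. This is worth correcting before the follow-up tables are produced; it does not touch the efficacy conclusions.

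**What to change.** - **Table (2).** Present all-grade AEs separately for children on sponsor rescue ETV, during rescue. For commercial ETV users report only SAEs and HBV-related diagnoses. SAP 8.9 derives a rescue start date only, so add a rescue end date from the rescue dosing CRFs.
- **Table (3).** Present by collection rule (rescue, no therapy, commercial), or limit the pooled table to SAEs and HBV-related diagnoses. Give the number of subjects under each rule. Stopping at the start of commercial therapy is not enough by itself: it largely repeats table (1) and leaves untreated children with study-drug-related AEs only.
- **Footnote.** State the collection rule under each table, including table (1), where untreated children are also only partly captured.
- **Reconcile** the Week 6 entry in Table 6.1 footnote e with Protocol 6.3.2 and 7.3.3, so that the rule in the footnotes is unambiguous.

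The cost is SAP wording, one derived date and a split of two descriptive tables. No new data are needed, because rescue dosing has its own CRF. The downside is smaller denominators in the split tables.
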